5.3.6.2. AML-Specific Dose-Limiting Toxicities

For patients enrolled in the AML arm, the DLT window of observation will be defined by the first 8 weeks from study entry/administration of first galinpepimut-S inoculation.

The occurrence of any of the following toxicities during the first 8 weeks (from the time of administration of the first galinpepimut-S inoculation), if assessed by the investigator to be reasonably possibly related to study drug, will be considered a DLT:

1. Missing > 25% of the doses of investigational agent(s) as a result of drug-related AE during cycle 1 and/or 2
2. Drug-related AE which causes patient to discontinue treatment during cycle 1 and/or 2
3. Grade 5 toxicity
4. Grade 4 non-hematological toxicity (other than laboratory abnormality)
5. Grade 3 non-hematological toxicity (other than laboratory abnormality; exception: fatigue, nausea, emesis, diarrhea, rash, infection, fever, or bleeding unless the event lasts more than 3 days despite optimal care)
6. Grade 3 and 4 non-hematological lab abnormality, if any of the following occurs:
 - a. Medical intervention is required
 - b. Abnormality persists > 1 week
 - c. Abnormality results in drug-induced liver injury
7. Any treatment-related toxicity that causes a greater than 3-week delay in initiation of cycle 2 and/or 3 (the latter cycle being the first one whereby galinpepimut-S and pembrolizumab are co-administered).
8. Development of an immune-related AE (irAE) resulting in withholding of pembrolizumab and initiation of steroids, for example, grade 2 or higher colitis/diarrhea, grade 2 or higher pneumonitis, grade 2 or higher transaminitis, any grade myocarditis (complete list currently shown in Table 5)

Any other toxicities in the AML arm will not be considered dose-limiting.

Staggered Early Enrollment:

To minimize exposing subjects to the risk of potential unknown acute and subacute toxicities of combining HMA with the investigational therapy (pembrolizumab and galinpepimut-S) in the AML arm, the inter-dosing interval between the first two (2) subjects to be enrolled in this study arm will be 12 weeks.

AML-specific DLT assessment and actions will be as follows (unless stopping rules apply):

- Initially up to 6 patients will be enrolled in the AML cohort. If 2 or fewer patients of these first 6 patients have DLTs, enrollment can continue for up to another 6 patients in the AML arm with no dose adjustments made. If DLTs are observed in more than 2 patients of the first 6, the time interval between galinpepimut-S doses for the inoculation following the one associated with the DLT will be doubled. For example, if galinpepimut-S was given on a Q3W schedule before the DLT occurred, it should be given Q6W for the immediately subsequent administration after the dosing event associated with the DLT, while keeping the pembrolizumab dose and frequency stable.
- In the next 6 patients (patients 7 to 12), if again, 2 or fewer of these patients have DLTs observed, enrollment can continue. If DLTs are observed in more than 2 of patients 7 to 12, the time interval between galinpepimut-S doses for the inoculation following the one associated with the DLT will be doubled, but pembrolizumab will continue as scheduled.
- If DLTs are observed in more than 2 patients of the first 6 (patients 1 to 6) and again in more than 2 patients of the next 6 (patients 7 to 12), the time interval between galinpepimut-S doses will be doubled for two (2) inoculations following the one associated with the DLT. For example, if galinpepimut-S was given on a Q3W schedule before the DLT occurred, it should be given Q6W for the 2 immediately subsequent administrations after the dosing event associated with the DLT, while keeping the pembrolizumab dose and frequency stable.

- If DLTs continue to be observed above 2 per every 6 patients beyond these first 12 patients, and even after the changes in administration of galinpepimut-S, the study will be stopped and the safety data will be examined by the sponsor in consultation with investigators in order to determine how to proceed or whether to discontinue the study.
- Should a given patient experience any of the above DLTs at any time after the completion of the first cycle of co-administration of galinpepimut-S in combination with pembrolizumab, the time interval between galinpepimut-S doses for the inoculation following the one associated with the DLT will be doubled, but pembrolizumab will continue as scheduled.
- If another DLT occurs in that next cycle, the time interval between galinpepimut-S doses will be doubled for two (2) inoculations following the one associated with the DLT, but pembrolizumab will continue as scheduled.
- If no DLTs re-occur after the above periods of doubly 'spaced out' administrations, then the patient should revert back to the initial GPS Q3W schedule (as per the initial dosing frequency/ investigational agent administration schedule).
- If a DLT occurs after these dose modifications in subsequent cycles, the patient will be discontinued from the study.

The above dose density modifications in response to DLTs is further summarized in the bulleted list of actions below:

- First DLT → skip the next GPS inoculation (scheduled for the next cycle, i.e., 3 wks ahead) and administer GPS 6 wks ahead (i.e., 'spread out') **once thereafter**, i.e. **for 1 additional cycle** → DLT resolution → Return to per protocol schedule of GPS administration
- Second DLT (after reverting to the per protocol schedule) → skip the next GPS inoculation (scheduled for the next cycle, i.e., 3 wks ahead) and administer GPS 6 wks ahead (i.e., 'spread out') **twice thereafter**, i.e. **for 2 additional cycles** → DLT resolution → Return to per protocol schedule of GPS administration

- Third DLT (occurring either after reverting to the per protocol schedule or during the ‘spread out’ schedule to manage the 2nd DLT above) → Discontinue patient from study.
- N.B.: In all above modifications of the dose density of galipepimut-S, as all intervals (in weeks) between 2 successive GPS administrations are multiples of three (3) by design, following these rules, co-administration with pembrolizumab is always secured.

Stopping rules (for AML patients):

- Development of any SAEs at least “possibly attributable” to the study agent(s) in 2 out of the first 6 patients in the study. In this case, the upper 90% one-sided CI bound for 2 patients with SAEs within 6 patients would be 66.7%, consistent with an excessive rate of toxicity.
- The fraction of patients experiencing an SAE at least “possibly attributable” to the study agent(s) exceeds 1/3, at any time during study implementation beyond the first 6 patients.
- Death at least “possibly attributable” to the study agent(s) within 30 days after the administration of the investigational treatment (GPS plus pembrolizumab)
- Development of grade 3 or higher colitis/diarrhea, grade 3 or higher pneumonitis, grade 3 or higher nephritis, grade 3 or higher transaminitis, or any grade myocarditis in 2 out of the first 6 patients in the AML arm of the study. In this case, the upper 90% one-sided CI bound for 2 patients with SAEs within 6 patients would be 66.7%, consistent with an excessive rate of toxicity.
- The fraction of patients experiencing grade 3 or higher colitis/diarrhea, grade 3 or higher pneumonitis, grade 3 or higher nephritis, grade 3 or higher transaminitis, or any grade myocarditis exceeds 40%, at any time during study implementation beyond the first 6 patients in the AML arm.

If the study is stopped due to activation of the above rules, the safety data will be examined by the sponsor in consultation with investigators in order to determine how to proceed or whether to discontinue the study at large.

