Treatments:

Patients will be administered a fixed dose of the following treatments:

- Galinpepimut-S: 4 WT1 derived synthetic analog peptides (galinpepimut-S) emulsified with the adjuvant Montanide for a total injection volume of 1 mL.
- Pembrolizumab: 200 mg

Patients will be administered subcutaneous (SC) sargramostim (from here on referred to as GM-CSF) at the site of the planned galinpepimut-S injection 2 days before (Day -2) and the day of (Day 1) each galinpepimut-S administration.

The overall treatment administration schedule is shown in the figure below:

Refer to [Section 5](#) for more details on treatment.

Dose-limiting Toxicities

All toxicities will be graded using NCI CTCAE Version 5.0 (published in November 2017), as per the following link:

https://ctep.cancer.gov/protocolDevelopment/electronic_applications/docs/CTCAE_v5_Quick_Reference_5x7.pdf.

The dose-limiting toxicity (DLT) window of observation will be:

For patients in the solid tumor arms: at least one (1) cycle following the co-administration of galipepimut-S in combination with pembrolizumab.

For patients in the AML arm: at least 8 weeks following the first administration of pembrolizumab

N.B.: this DLT assessment time window at the beginning of the study was chosen considering that (i). the treatment regimen in AML subjects includes the administration of HMA treatment (with cycle duration of at least 4 weeks), along with investigational therapy (pembrolizumab and galipepimut-S), and (ii). the timing of administration of the two sets of modalities is not linked, so that an adequate time interval to capture potential toxicities is secured.

A DLT is judged by the investigator to be possibly, probably, or definitely related to study drug administration.

For patients in the solid tumor arms:

Missing > 25% of the doses as a result of drug-related AE(s) during the period from first administration of galipepimut-S

and up until the completion of the first cycle of the co-administration of galinpepimut-S in combination with pembrolizumab, drug-related AE(s) which caused patient to discontinue treatment during Cycle 1, or Grade 5 toxicity, will be considered DLTs.

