- Second DLT (after reverting to the per protocol schedule) → skip the next GPS inoculation (scheduled for the next cycle, i.e., 3 wks ahead) and administer GPS 6 wks ahead (i.e., ‘spread out’) **twice thereafter**, i.e. **for 2 additional cycles** → DLT resolution → Return to per protocol schedule of GPS administration
- Third DLT (occurring either after reverting to the per protocol schedule or during the ‘spread out’ schedule to manage the 2nd DLT above) → Discontinue patient from study.

N.B.: In all above modifications of the dose density of galinpepimut-S, as all intervals (in weeks) between 2 successive GPS administrations are multiples of three (3) by design, following these rules, co-administration with pembrolizumab is always secured.

Stopping Rules:

- Development of any SAEs at least “possibly attributable” to the study agent(s) in 2 out of the first 6 patients in the study. In this case, the upper 90% one-sided CI bound for 2 patients with SAEs within 6 patients would be 66.7%, consistent with an excessive rate of toxicity.
- The fraction of patients experiencing an SAE at least “possibly attributable” to the study agent(s) exceeds 1/3, at any time during study implementation beyond the first 6 patients.
- Death at least “possibly attributable” to the study agent(s) within 30 days after the administration of the investigational treatment (GPS plus pembrolizumab).

If the study is stopped due to activation of the above rules, the safety data will be examined by the sponsor in consultation with investigators in order to determine how to proceed or whether to discontinue the study at large.

For patients in the AML arm:DLTs will be defined by toxicities observed in the first 8 weeks from study entry, as follows:

- a. Missing > 25% of the doses as a result of drug related AE during cycle 1 and/or 2

b. Drug-related AE which causes patient to discontinue treatment during cycle 1 and/or 2

- Grade 5 toxicity
- Grade 4 non-hematological toxicity (other than laboratory abnormality)
- Grade 3 non-hematological toxicity (other than laboratory abnormality; exception: fatigue, nausea, emesis, diarrhea, rash, infection, fever, or bleeding unless the event lasts more than 3 days despite optimal care)
- Grade 3 and 4 non-hematological lab abnormality, if any of the following occurs:
 - Medical intervention is required
 - Abnormality persists > 1 week
 - Abnormality results in drug-induced liver injury

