 - Any treatment-related toxicity that causes a greater than 3-week delay in initiation of cycle 2 and/or 3
 - Development of an immune-related AE resulting in withholding of pembrolizumab and initiation of steroids, for example, grade 2 or higher colitis/diarrhea, grade 2 or higher pneumonitis, grade 2 or higher transaminitis, any grade myocarditis (complete list currently shown in Table 5)

Any other toxicities in the AML arm will not be considered dose-limiting. Details for AML DLTs are provided in [Section 5.3.6.2](#).

Staggered Early Enrollment:

To minimize exposing subjects to the risk of potential unknown acute and subacute toxicities of combining HMA with the investigational therapy (pembrolizumab and galinpepimut-S) in the AML arm, the inter-dosing interval between the first two (2) subjects to be enrolled in this study arm will be 12 weeks.

DLT assessment and actions (unless stopping rules apply):

AML-specific DLTs will be considered separately from all other patients. Initially up to 6 patients will be enrolled in the AML cohort. If 2 or fewer patients of these first 6 patients have DLTs, enrollment can continue for up to another 6 patients in the AML arm with no dose adjustments made. If DLTs are observed in more than 2 patients of the first 6, the time interval between galinpepimut-S doses will be doubled for the inoculation following the one associated with the DLT, but pembrolizumab will continue as scheduled.

In the next 6 patients (patients 7 to 12), if again, 2 or fewer of these patients have DLTs observed, enrollment can continue. If DLTs are observed in more than 2 of patients 7 to 12, If DLTs are observed in more than 2 of patients 7 to 12, the time interval between galinpepimut-S doses will be doubled for the inoculation following the one associated with the DLT, but pembrolizumab will continue as scheduled.

If DLTs are observed in more than 2 patients of the first 6 (patients 1 to 6) and again in more than 2 patients of the next 6 (patients 7 to 12), the time interval between galinpepimut-S doses will be doubled for two (2) inoculations following the one associated with the DLT, but pembrolizumab will continue as scheduled. For example, if galinpepimut-S was given on a Q3W

schedule before the DLT occurred, it should be given Q6W for the 2 immediately subsequent administrations after the dosing event associated with the DLT, while keeping the pembrolizumab dose and frequency stable.

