3.1.1. Overall Treatment Investigational Administration Schedule

Patients will receive 70 µg sargramostim (GM-CSF) SC on Day -2 and on Day 1 before each galinpepimut-S injection. The first GM-CSF injection of each doublet will occur at the same anatomical site of the planned galinpepimut-S treatment injection within each given cycle.

The first 2 galinpepimut-S injections will initially be administered as monotherapy every 3 weeks (Week 0 and Week 3). Thereafter, galinpepimut-S will be co-administered with pembrolizumab every 3 weeks for 4 additional administrations (for the galinpepimut-S initial immunization induction phase series; weeks 6-15) to coincide with the per label pembrolizumab dosing frequency. After that, there will be one un-paired administration of pembrolizumab (week 18), and then galinpepimut-S will be resumed on an every 3-week schedule for 6 additional doses (early immune booster phase; weeks 21-36). At the end of this phase, there will be a 12-week interval where 3 unpaired administrations of

pembrolizumab will occur (weeks 39-45), and then galinpepimut-S will be resumed on an every 12-week schedule for 4 additional doses (late immune booster phase; weeks 48-84). After 84 weeks, continuing non-progressed patients will be treated with pembrolizumab alone up until week 111. Galinpepimut-S will be administered 30-60 minutes after the completion of IV infusion of pembrolizumab on Day 1 of each cycle during which the 2 drugs are being co-administered.

Pembrolizumab will be administered at a dose of 200 mg intravenously every 3 weeks on Day 1 of each cycle (3-week cycles) starting on Study Week 6 and continuing for up to 2 years thereafter (Study Week 111). To monitor for any adverse reactions, specifically for systemic anaphylaxis type reactions against either GM-CSF or galinpepimut-S, patients will remain in the clinic for approximately 30 minutes following each GM-CSF or galinpepimut-S injection. Safety assessments will be conducted at every visit. The end of treatment (EOT) visit will occur 30 days after the last injection.

Specifically for patients in the AML arm, the timing of the administration of the investigational therapies (pembrolizumab and galinpepimut-S) with respect to administration of hypomethylating agents (HMAs) will be as follows:

- AML patients on cycles #1 – 4 of HMA on-label therapy (treated according to standard clinical care) will be pre-screened to gauge potential eligibility for the study.

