5.3.6.1. Dose-Limiting Toxicities

All toxicities will be graded using National Cancer Institute Common Terminology Criteria for Adverse Events (NCI CTCAE) Version 5.0, (published in November 2017), as per the following link:

https://ctep.cancer.gov/protocolDevelopment/electronic_applications/docs/CTCAE_v5_Quick_Reference_5x7.pdf.

For patients enrolled across all active solid tumor cohorts (colorectal, ovarian, small cell lung cancer, breast cancer), the dose-limiting toxicity (DLT) window of observation will be at least one (1) cycle following the co-administration of galinpepimut-S in combination with pembrolizumab. A DLT is judged by the investigator to be possibly, probably, or definitely related to study drug administration. AML-specific DLTs will be considered separately ([Section 5.3.6.2](#)).

The occurrence of any of the following toxicities will be considered a DLT (except for AML; please see [Section 5.3.6.2](#)), if judged by the investigator to be possibly, probably, or definitely related to study drug administration:

1. Grade 4 nonhematologic toxicity (not laboratory)
2. Grade 4 hematologic toxicity lasting ≥ 7 days, except thrombocytopenia:
 - Grade 4 thrombocytopenia of any duration
 - Grade 3 thrombocytopenia associated with bleeding
3. Any nonhematologic AE \geq Grade 3 in severity should be considered a DLT, with the following exceptions: Grade 3 fatigue lasting ≤ 3 days; Grade 3 diarrhea, nausea, or vomiting without use of anti-emetics or anti-diarrheals per standard of care; Grade 3 rash without use of corticosteroids or anti-inflammatory agents per standard of care.
4. Grade 3 nonhematologic toxicity (not laboratory) lasting > 3 days despite optimal supportive care.
5. Any Grade 3 or Grade 4 nonhematologic laboratory value if:

- Clinically significant medical intervention is required to treat the patient, or
 - The abnormality leads to hospitalization, or
 - The abnormality persists for > 1 week.
 - The abnormality results in a drug-induced liver injury (DILI)
 - Exceptions: clinically nonsignificant, treatable, or reversible laboratory abnormalities, including liver tests, uric acid, etc.
6. Febrile neutropenia (FN) Grade 3 or Grade 4:
 - Grade 3 is defined as absolute neutrophil count (ANC) < 1000/mm³ with a single temperature of > 38.3°C (101°F) or a sustained temperature of ≥ 38°C (100.4°F) for more than 1 hour

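### The AML dose-limiting toxicity window ends at Week 8 in one place and at Week 14 or later in another; the Week 8 window sees only two weeks and one pembrolizumab dose of the combination

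*Combined protocol and SAP*

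**What the plan says.** The window is defined in three places, all current text.

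- **Synopsis, Dose-limiting Toxicities:** "For patients in the AML arm: at least 8 weeks following the first administration of pembrolizumab". A note explains the choice. AML patients also receive "HMA treatment (with cycle duration of at least 4 weeks"), its timing is not linked to study therapy, and the window was set "so that an adequate time interval to capture potential toxicities is secured".
- **Synopsis, DLTs for the AML arm:** "DLTs will be defined by toxicities observed in the first 8 weeks from study entry". This part ends with "Details for AML DLTs are provided in" Section 5.3.6.2.
- **Section 5.3.6.2:** "the DLT window of observation will be defined by the first 8 weeks from study entry/administration of first galinpepimut-S inoculation". The sentence introducing the criteria repeats the first-galinpepimut-S anchor.

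Under Section 3.1.1, galinpepimut-S is given alone at Weeks 0 and 3, and pembrolizumab is given every 3 weeks, "starting on Study Week 6 and continuing for up to 2 years thereafter". For solid tumors, Section 5.3.6.1 asks for "at least one (1) cycle following the co-administration of galinpepimut-S in combination with pembrolizumab".

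The count is used in Section 5.3.6.2. If 2 or fewer of the first 6 AML patients have a DLT, enrollment continues without dose adjustment. If more than 2 do, galinpepimut-S spacing is doubled for one inoculation. The same rule applies to patients 7 to 12, and exceeding 2 in both groups doubles the spacing for two inoculations.

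**The concern.** The two anchors lie 6 weeks apart, and most of that gap is the period in which the triple combination of HMA, galinpepimut-S and pembrolizumab is first given. The words 'at least' in the synopsis do not bridge it: one statement is a minimum from first pembrolizumab, the other a fixed period from first galinpepimut-S. Because the synopsis sends the reader to Section 5.3.6.2 for details, a site would probably apply the Week 8 window, which is the one that fits the stated rationale worst.

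At stake is the cohort DLT count. Take grade 2 pneumonitis at Week 10. Table 5 has pembrolizumab withheld and corticosteroids given, so it meets AML criterion 8. It falls inside the synopsis window and outside the Section 5.3.6.2 window. Section 5.3.6.3.1 says immune-related events can appear from shortly after the first dose to months after the last, so such timing is expected. Sections 6.5 and 10.1 provide no safety committee and no external data monitoring committee that could settle the reading, so the written rule has to.

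**Working it through.** **Inputs.** Galinpepimut-S is due at Weeks 0, 3, 6, 9 and 12, and pembrolizumab at Weeks 6, 9 and 12 (Section 3.1.1). The study cycle is 3 weeks. The HMA cycle is at least 4 weeks (synopsis). Week 0 is first galinpepimut-S. Study entry is a few days earlier, which changes nothing below.

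**Window ends.** Section 5.3.6.2: 0 + 8 = Week 8. Synopsis window paragraph: 6 + 8 = Week 14 at the earliest. Difference: 14 − 8 = 6 weeks.

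| | Section 5.3.6.2 (Weeks 0 to 8) | Synopsis (Weeks 6 to 14) |
|---|---|---|
| Weeks on combination | 8 − 6 = 2 | 14 − 6 = 8 |
| Pembrolizumab doses | 1 (Week 6) | 3 (Weeks 6, 9, 12) |
| Galinpepimut-S doses | 3 (Weeks 0, 3, 6) | 3 (Weeks 6, 9, 12) |
| 3-week study cycles on combination | 2/3 = 0.67 | 8/3 = 2.67 |
| HMA cycles during combination | at most 2/4 = 0.5 | at most 8/4 = 2 |

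The Week 8 window therefore holds 2/8 = 25% of the combination time of the other. The solid-tumor minimum is one cycle from Week 6, or 3 weeks, so AML patients would be observed for less, with an extra drug on board.

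**If first pembrolizumab slips by d weeks.** Combination weeks inside the Week 8 window are max(0, 8 − (6 + d)): 2 for d = 0, 1 for d = 1, and 0 for d = 2 or 3. Criterion 7 counts only delays of more than 3 weeks. A patient whose cycle 3 starts 2 to 3 weeks late can thus finish the window free of DLTs with essentially no combination exposure. Criteria 1 and 2 do not catch this, because they cover cycles 1 and 2, before any pembrolizumab.

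**Stagger.** Section 5.3.6.2 puts 12 weeks between the first two AML patients. If this is counted first dose to first dose, patient 1 has had 12 − 6 = 6 weeks of combination when patient 2 starts. That is 14 − 12 = 2 weeks short of the end of a Week 14 window.

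**The case against.** The best defence is that the Week 8 window does little damage because so much acts outside it.

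- The SAE, death and AML immune-toxicity stopping rules in Section 5.3.6.2 are not tied to 8 weeks.
- Table 5 withholds or stops pembrolizumab for immune-related events at any time.
- DLTs after the early co-administration cycles still trigger wider galinpepimut-S spacing for that patient.
- The 12-week stagger protects the second AML patient.
- The cohort count changes only galinpepimut-S spacing. Pembrolizumab continues as scheduled, and exceeding 2 of 6 does not expressly halt enrollment. The study-stop rule beyond patient 12 reaches only 15 − 12 = 3 of the planned AML patients.

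All of this stands and limits the consequence. It does not make the two windows agree.

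It can also be said that the sponsor may have meant the entry-anchored window: the synopsis note speaks of the start of the study, and criteria 1, 2 and 7 refer to early cycles. That is possible. Correcting the synopsis would remove the contradiction but leave a window that does not do what the synopsis says it is for.

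Finally, the first-6 rule carries no date, and the same list calls later events DLTs, so excluding a Week 10 event is the natural reading of Section 5.3.6.2 but not the only one. That ambiguity is a further reason to fix the text.

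**Conclusion.** The inconsistency is real and should be fixed. The AML window ends at Week 8 or at Week 14 or later depending on the page. On schedule, that is 2 against 8 weeks of combination and 1 against 3 pembrolizumab doses. The shorter window falls below the solid-tumor minimum and runs against the plan's own rationale. The figures assume on-schedule dosing; a slip of 2 weeks or more in first pembrolizumab leaves the Week 8 window with essentially no combination exposure.

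Three stronger readings are not supported:

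- **Late toxicity escapes all action.** It does not, given the stopping rules, Table 5 and per-patient spacing. What depends on the window is mainly the cohort count of toxicity below the stopping rules.
- **The longer window also sees more galinpepimut-S, 5 doses against 3.** The synopsis window opens at first pembrolizumab, so each documented window holds 3. Five is right only if Weeks 0 and 3 are added to it.
- **A given probability of missing a DLT signal.** The documents state no AML DLT risk, so any such figure would rest on an assumed risk and hazard.

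**What to change.** Use one sentence in the synopsis window paragraph, the synopsis AML DLT definition and Section 5.3.6.2: *The AML DLT window runs from first galinpepimut-S through 8 weeks after the patient's actual first pembrolizumab dose (Week 14 on schedule).* Anchoring to the actual dose keeps the combination period intact if pembrolizumab slips.

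Three changes go with it:

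- Let criteria 1, 2 and 7 also cover the combination cycles that start inside the window (cycles 3 to 5, Weeks 6, 9 and 12).
- Take the first-6 and patients 7 to 12 decisions only after each of those patients has completed the window, had a DLT or left treatment.
- Recheck the 12-week stagger and state what it is counted from.

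Finer rules, such as counting missed doses by agent or rewriting per-patient spacing, are optional.

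The cost is one amendment with IRB approval (Section 10.3.1) and a first-6 decision about 14 − 8 = 6 weeks later than with the Week 8 window. It is somewhat longer if a criterion 7 delay is still pending. A late cycle 5, due at Week 12, passes the 3-week limit only after Week 15, about 1 week beyond the window.

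### AML arm: the DLT window is stated in two incompatible ways, and the Week 8 version counts only 14 days of the combination toward the six-patient gates

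*Combined protocol and SAP*

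**What the plan says.** The AML window appears three times in current text.

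- Protocol Synopsis, opening paragraph on dose-limiting toxicities: "at least 8 weeks following the first administration of pembrolizumab". The note beneath gives the reason. HMA cycles last at least 4 weeks and are not linked in time to the study agents, so the interval was chosen "so that an adequate time interval to capture potential toxicities is secured".
- Protocol Synopsis, AML list of DLTs: "DLTs will be defined by toxicities observed in the first 8 weeks from study entry".
- Section 5.3.6.2: "the DLT window of observation will be defined by the first 8 weeks from study entry". The section treats study entry and first galinpepimut-S as the same anchor, and its next sentence repeats the galinpepimut-S anchor.

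Section 3.1.1 gives galinpepimut-S alone at Weeks 0 and 3. Pembrolizumab then follows on "Day 1 of each cycle (3-week cycles) starting on Study Week 6". AML cycles are 3 weeks long.

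One listed DLT is "Any treatment-related toxicity that causes a greater than 3-week delay in initiation of cycle 2 and/or 3". Section 5.3.6.2, item 7, adds of cycle 3: "the latter cycle being the first one whereby" the two agents are given together.

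The counts feed two gates: more than 2 DLT patients among patients 1 to 6, and more than 2 among patients 7 to 12. Section 5.3.6.2 also stops the study if that rate continues beyond the first 12. The synopsis starts the AML per-patient rule after the second combination cycle, whereas Section 5.3.6.2 starts it after the first.

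**The concern.** The two anchors are 6 weeks apart, and those 6 weeks are the galinpepimut-S-only run-in. A clock started at first galinpepimut-S uses most of its 8 weeks before the patient receives any pembrolizumab. The gates are meant to show whether galinpepimut-S plus pembrolizumab, added to continuing HMA, is tolerable. Under the Week 8 window they mostly observe galinpepimut-S plus HMA.

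The same patient can therefore count as a DLT under one statement and not under the other. Take a Grade 2 immune-related event at Week 10 that leads to a pembrolizumab hold and steroids. It falls inside the first synopsis window and outside the window in Section 5.3.6.2. Section 5.3.6.3.1 itself warns that immune-related events can appear long after dosing. Sections 6.5 and 10.1 provide no safety or data monitoring committee that could settle the count.

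**Working it through.** No power or alpha figure is involved, so the check is calendar arithmetic. Week 0 is first galinpepimut-S.

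Inputs: galinpepimut-S alone at Weeks 0 and 3, and first pembrolizumab (start of cycle 3) at Week 6 (Section 3.1.1). Window length is 8 weeks. The delay DLT needs more than 3 weeks. An HMA cycle is at least 4 weeks, or 28 days (synopsis note).

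| | Anchored on first pembrolizumab (synopsis, opening DLT paragraph) | Anchored on entry or first galinpepimut-S (synopsis AML list; Section 5.3.6.2) |
|---|---|---|
| Window closes | 6 + 8 = Week 14 at the earliest | 0 + 8 = Week 8 |
| Combination time covered | (14 − 6) × 7 = 56 days or more | (8 − 6) × 7 = 14 days |
| Co-administrations covered | 3 (Weeks 6, 9, 12) | 1 (Week 6) |

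The shorter window covers 14/56 = 25% of the minimum combination time in the longer one. It is also half of the shortest HMA cycle (14/28). If study entry means the baseline visit, the Week 8 window closes two to three days earlier still.

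Delay item:
- Cycle 2 is due at Week 3, so a delay of more than 3 weeks is known just after 3 + 3 = Week 6. This is inside the Week 8 window.
- Cycle 3 is due at Week 6, so the same delay is known just after 6 + 3 = Week 9. This is about one week after the Week 8 close and inside the Week 14 window.

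Per-patient rule: combination cycle 1 ends at 6 + 3 = Week 9 (the start in Section 5.3.6.2). Combination cycle 2 ends at 6 + 6 = Week 12 (the start in the synopsis). The two texts differ by 3 weeks.

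Enrollment stagger: with 12 weeks between the first two AML patients, counted from first dosing, patient 2 first receives pembrolizumab at 12 + 6 = Week 18 on patient 1's clock. That is after patient 1's Week 14 close, so the longer window does not disturb the stagger.

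**The case against.** One defence is that Section 5.3.6.2 governs. The synopsis refers the reader there for AML details, and one of the two synopsis statements agrees with it. That settles which text a site would probably follow. It does not remove the conflict, and it leaves in force the version that fails the synopsis's own stated purpose.

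The stronger objections concern consequences that a reader might infer, and they largely stand.

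- **A cap on what can ever be a DLT.** The sentence "Any other toxicities in the AML arm will not be considered dose-limiting" could be read as excluding everything after Week 8. It closes a list of toxicity types, so its natural meaning is types that are not listed. Both texts of the per-patient rule apply the listed DLTs to later events. Only the gate count is limited by time.
- **The cycle 3 delay is lost as a DLT.** A toxicity that prevents dosing at Week 6 would normally be present by then, inside the window. Only confirmation of the delay falls after Week 9. The text does not say how to score it, which is a scoring lag and not a proven omission.
- **A period with no rule at all.** The start dates of the per-patient rule suggest a gap between Week 8 and Week 9 or 12. However, the bulleted summaries of action after a first, second and third DLT carry no start date and can be read as covering it.
- **Loss of safety control.** More than 2 of the first 6 leads to doubling of the next galinpepimut-S interval with pembrolizumab unchanged, which the per-patient rule already does. The rules on related SAEs and the AML immune-event rules (Grade 3 or higher, or any myocarditis) trigger at 2 of the first 6, a lower count, and are not tied to the DLT window. Neither is the rule on related deaths. The Table 5 holds also continue.
- **The same defect in the solid-tumor arms.** Their window is a minimum of one combination cycle and contradicts nothing.

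**Conclusion.** The contradiction is real and should be fixed. The AML window closes either at Week 8 or no earlier than Week 14, with no text to choose between them. The Week 8 version counts 14 days and one co-administration, against at least 56 days and three.

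The effect is bounded. It changes which events enter the gate counts, mainly Grade 2 immune-related events with a hold and steroids, and non-serious Grade 3 events outside the organs named in the immune-event stopping rules. Through those counts it can change the doubling of two successive galinpepimut-S intervals after both gates, and the DLT-based stop beyond patient 12. With 15 AML patients planned, that stop concerns 15 − 12 = 3 patients unless the cohort is expanded.

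A reader might want a figure for the lost sensitivity of the gate. The documents give no DLT rates and no time pattern, so none is supported. The conclusion rests only on the dosing calendar and on patients starting pembrolizumab on schedule.

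**What to change.** In both synopsis statements and in Section 5.3.6.2, use one AML window: from first galinpepimut-S through at least 8 weeks after that patient's first pembrolizumab, nominally Week 14. Starting at first galinpepimut-S keeps the run-in weeks in the count. Anchoring the end on the patient's own first pembrolizumab secures the exposure the synopsis intends even if dosing is late.

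Add to item 7 that a toxicity-related cycle 3 delay is scored as a DLT once it exceeds 3 weeks. Align the start of the AML per-patient rule in the synopsis with Section 5.3.6.2, that is, after the first combination cycle.

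The cost is wording, with no extra patients or procedures. The window closes 14 − 8 = 6 weeks later than Section 5.3.6.2 now states, so up to about 6 weeks at each six-patient gate if enrollment waits there. The first synopsis statement already implies that wait. The 12-week stagger can stay.
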